5. STUDY OBJECTIVES

5.1 Primary Objective

The primary objective of this trial is to evaluate the safety of PRX-102 in patients with Fabry disease currently treated with agalsidase alfa.

5.2 Secondary Objectives

The secondary objective of this trial is to evaluate the efficacy of PRX-102 in patients with Fabry disease currently treated with agalsidase alfa.

6. INVESTIGATIONAL PLAN

6.1 Overall Study Design and Plan – Description

This is an open label switch over study to assess the safety and efficacy of PRX-102. Patients treated with agalsidase alfa for at least 2 years and on a stable dose (>80% labelled dose/kg/) for at least 6 months. Patients will enter the study for 3 month Screening period for baseline data generation. Eligible patients will be switched from their agalsidase alfa treatment to receive intravenous (IV) infusions of PRX-102 1 mg/kg every two weeks for 12 months. No more than 25% of treated patients will be female.

At the time of enrolment, premedication, if used for the agalsidase alfa infusions before study entry, will be continued during the Screening period and to the first infusion with PRX-102 treatment and then gradually tapered at the investigator's discretion during the first 2 months. The first infusions of PRX-102 will be administered under controlled conditions at the investigation site. The patient can receive their PRX-102 infusions at a home care setup once the investigator and Sponsor Medical Director agree that it is safe to do so.

6.2 Discussion of Study Design and Choice of Control Group(s)

This is a Phase 3, open-label, switchover study to assess the safety and efficacy of PRX-102 (pegunigalsidase alfa) in patients with Fabry disease who have been treated with agalsidase alfa (Replagal[®]) ERT. The dose of pegunigalsidase alfa is 1 mg/kg and switching from agalsidase alfa is an appropriate study design in this rare disease population.

PRX-102 and agalsidase alfa are different products and immunogenicity and hypersensitivity may be different between the products. Premedication to prevent adverse reactions during infusion is administered in some patients receiving agalsidase alfa. Because the requirements for premedication may be different between the two products, premedication will be tapered off, as tolerated, over the initial 2 months of infusions under careful observation after switching to PRX-102. Premedication to prevent infusion reactions can be maintained or re-introduced as required.

6.3 Selection of Study Population

6.3.1 Inclusion Criteria

The subjects must meet the following inclusion criteria:

1. Age: 18-60 years
2. A documented diagnosis of Fabry disease

3. Males: plasma and/or leucocyte alpha galactosidase activity (by activity assay) less than lower limit of normal according to laboratory range and one or more of the characteristic features of Fabry disease
 - i. Neuropathic pain
 - ii. Cornea verticillata
 - iii. Clustered angiokeratoma
4. Females: historical genetic test results consistent with Fabry mutations, or in the case of novel mutations a first degree male relative with Fabry disease, and one or more of the characteristic features of Fabry disease
 - i. Neuropathic pain
 - ii. Cornea verticillata
 - iii. Clustered angiokeratoma
5. Treatment with agalsidase alfa for at least 2 years and on a stable dose (>80% labelled dose/kg) for at least 6 months
6. $eGFR \geq 40$ ml/min/1.73 m² by CKD-EPI equation
7. Availability of at least 2 historical serum creatinine evaluations since starting agalsidase alfa treatment and not more than 2 years
8. Female patients and male patients whose co-partners are of child-bearing potential agree to use a medically acceptable method of contraception, not including the rhythm method

6.3.2 Exclusion Criteria

The presence of any of the following excludes a subject from study enrollment:

1. History of anaphylaxis or Type 1 hypersensitivity reaction to agalsidase alfa
2. History of renal dialysis or transplantation
3. History of acute kidney injury in the 12 months prior to screening, including specific kidney diseases (e.g., acute interstitial nephritis, acute glomerular and vasculitic renal diseases); non-specific conditions (e.g, ischemia, toxic injury); as well as extrarenal pathology (e.g., prerenal azotemia, and acute postrenal obstructive nephropathy)
4. Angiotensin converting enzyme (ACE) inhibitor or angiotensin receptor blocker (ARB) therapy initiated or dose changed in the 4 weeks prior to screening
5. Urine protein to creatinine ratio (UPCR) > 0.5 g/g and not treated with an ACE inhibitor or ARB
6. Known history of hypersensitivity to Gadolinium contrast agent that is not managed by the use of premedication
7. Females who are pregnant, planning to become pregnant during the study, or are breast feeding
8. Cardiovascular event (myocardial infarction, unstable angina) in the 6 month period before screening
9. Congestive heart failure NYHA Class IV
10. Cerebrovascular event (stroke, transient ischemic attack) in the 6 month period before screening

-
11. Presence of any medical, emotional, behavioral or psychological condition that, in the judgment of the Investigator and/or Medical Director, would interfere with the patient's compliance with the requirements of the study

6.3.3 Removal of Subjects from Therapy or Assessment

Reasons for permanent discontinuation include the following:

- The subject experiences two or more Grade 3 toxicities or one or more Grade 4 toxicity considered by the investigator associated with PRX-102 (CTCAE v. 4.03, 2010)
- The subject experiences progressive hypersensitivity or severe hypersensitivity that is not allayed with pre-treatment
- The subject requests to discontinue treatment
- The Investigator feels that it is not in the best interest of the subject to continue treatment and/or if the investigator believes that the subject can no longer be compliant with the requirements of the study

For any discontinuation, the Investigator will obtain all the required details and document the date and the main reason for the premature termination. If the reason for discontinuation is an adverse event, the specific event or the main laboratory abnormality will be recorded in the eCRF. The Investigator will make thorough efforts to document the outcome. The Investigator will attempt to continue to follow the subject for the full duration of the study or at least for 90 days following discontinuation. If circumstances prevent the subject from completing all visits, every attempt will be made to complete all procedures listed in Section 9 for Visit 27.

6.3.4 Replacement Policy

Withdrawn patients will not be replaced.

7. STUDY PRODUCT

7.1 Study Medication Supply

Protalix will provide PRX-102 to the sites as needed.

7.2 Description of Study Product

PRX-102 is a purified recombinant, plant cell-expressed chemically modified human alpha galactosidase, which is described in detail in the Investigator's Brochure.

Each vial contains 10.2 ml of the following contents in liquid form:

20 mg PRX-102 (2mg/ml)
0.7% NaCl
25-30 mM Sodium Citrate (pH 5.7 - 6.3).

7.3 Study drug dosage and preparation

PRX-102 1 mg/kg; the individual dose for each patient will be prepared according to the patient's weight.

Dose of PRX-102 will be adjusted at visit 14 (6 months on pegunigalsidase alfa treatment) if the weight changes by 25% from first infusion.

Each dose will be prepared by a pharmacist or nurse at each site.

The required amount of PRX-102 will be adjusted with normal saline (0.9% NaCl) to a final volume of :

150 mL/infusion, for patients weighting up to 70 Kg

250 mL/infusion, for patients weighting between 70 Kg-100Kg

500 ml/infusion for patients weighting above 100 Kg

The infusion Volume will be recalculated , only if the dosage adjustment was performed.

7.4 Study Drug Administration

PRX-102 will be administered by intravenous infusion over 3 hours (0.83 mL/min). After 3 months of infusions, if the patient is tolerating the infusions well, the infusion time may be reduced gradually to 1.5 hours based on investigator evaluation and Protalix Medical Director approval. The patient will be clinically observed for 2 hours post dosing when under PRX-102. Observation period may be shorten to 1 hour pending patient tolerability per investigator discretion and after Medical Monitor approval.

At any time the infusion rate may be adjusted according to individual subject's signs and symptoms (see Appendix 2).

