TEST PRODUCT(S), DOSE AND MODE OF ADMINISTRATION: During the first 3 months (Screening period), patients will be on agalsidase alfa according to their previous regimen (dose, frequency and rate of infusion). Upon confirmation of eligibility, patients will be switched to PRX-102 1 mg/kg, intravenously to be administered over 3 hours, every 2 weeks. After the first 2 months of treatment with PRX-102, infusion time may be reduced gradually to 1.5 hours pending patient tolerability, investigator evaluation, and Sponsor Medical Monitor/Director approval.

STUDY DURATION: Total 15 months, with 3 months Screening while on agalsidase alfa and 12 months Treatment on PRX-102, with the option to be enrolled in an extension study upon completion of this study.

DISCONTINUATION FROM TREATMENT:

Reasons for permanent discontinuation include the following:

- The subject experiences two or more Grade 3 toxicities or one or more Grade 4 toxicity considered by the investigator associated with PRX-102 treatment (CTCAE v. 4.03, 2010)
- The subject experiences progressive hypersensitivity or severe hypersensitivity that is not allayed with pre-treatment
- The subject requests to discontinue treatment
- The Investigator feels that it is not in the best interest of the subject to continue treatment and/or if the investigator believes that the subject can no longer be compliant with the requirements of the study

SAFETY ENDPOINTS:

Change from baseline in:

- Clinical laboratory tests
- Physical examination
- Assessment of the injection site
- Electrocardiogram
- Treatment-emergent adverse events
- Ability to taper off infusion premedication throughout the first 2 months of the study
- Requirement for use of premedication overall to manage infusion reactions
- Treatment-emergent anti-PRX-102 antibodies

EFFICACY ENDPOINTS:

- Mean annualised change in estimated glomerular filtration rate (eGFR_{CKD-EPI})

- Left Ventricular Mass Index (g/m^2) preferably by MRI (echocardiogram can be used as an alternative)
- Plasma Lyso-Gb3
- Plasma Gb3
- Urine Lyso-Gb3
- Protein/Creatinine ratio spot urine test
- Frequency of pain medication use
- Exercise tolerance (Stress Test)
- Short Form Brief Pain Inventory (BPI)
- Mainz Severity Score Index (MSSI)
- Quality of life EQ-5D-5L

STATISTICAL ANALYSIS:

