14.2 Appendix 2. Infusion Rate Algorithm

[figure not shown]
The infusion rate (IR) may be adjusted according to individual subject symptoms and signs. The infusion rate will be adjusted according to Section 7.4 Study Drug Administration under the direction of the Investigator and Protalix Medical director. Premedications if given when under agalsidase alfa will be tapered gradually during the first 2 months when under PRX-102 under the direction of the Investigator and Protalix Medical Director (See Appendix 8). The assumptions with respect to adverse experiences to the infusion are:

1. Most of the subjects will tolerate the infusion without any special symptom or event.
2. Subjects presenting symptoms and signs of **severe** hypersensitivity will be evaluated according to the CTCAE Drug Toxicity criteria and there may be a discontinuation of treatment according to the protocol.
3. Subjects may present signs and symptoms that will respond to reducing the infusion rate and may not appear at the next infusion.
4. Tolerability and the subject specific infusion rate will be assessed and decided by the Investigator according to vital signs and clinical status of the subject.

Definitions to be applied regarding tolerability of infusions are as follows:

Good tolerability	Partial tolerability	Poor tolerability
Infusion was performed without signs and symptoms (such as burning, pruritus, flushing, discomfort, or change in vital signs).	Signs and symptoms appeared during the infusion and resolved after slowing infusion rate or at the end of the infusion.	Signs and symptoms meeting the definitions of CTCAE Grade 1 or 2 toxicity responding to reduction of infusion rate or responding to treatment (example, antihistamine for urticaria).

The specific algorithm for other infusion rate changes to be followed:

Changes in infusion rates according to the protocol:

The tolerability of the infusions in these patients will be determined by signs and symptoms during the infusion, and observation in the hospital, and by telephone contact the day after the infusion.

For patients with good tolerability after the first 2 months of treatment and the finalization of the attempt of premedication discontinuation (in patients who were previously on premedication) the time of infusion can be decreased by 30 minutes every third infusion, up to a minimum infusion time of 1.5 hours under the agreement between the Investigator and the Medical Director.

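### Protocol 7.4 gives all patients one rate, 0.83 mL/min, for a 3-hour infusion, but that rate takes 3 hours only for the 150 mL volume used up to 70 kg

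*Protocol*

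**What the plan says.** Protocol 7.3 fixes the final infusion volume by body weight in three bands:

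- in the lightest band, "150 mL/infusion, for patients weighting up to 70 Kg"
- in the middle band, from 70 to 100 kg, a volume of 250 mL
- in the heaviest band, "500 ml/infusion for patients weighting above 100 Kg"

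The volume is recalculated later only if the dose itself is adjusted.

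Protocol 7.4 then gives one duration and one rate for everyone: "PRX-102 will be administered by intravenous infusion over 3 hours (0.83 mL/min"). It allows the rate to be changed for a patient's signs and symptoms, but says nothing about changing it for volume.

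The Synopsis gives the duration without a rate: "intravenously to be administered over 3 hours, every 2 weeks". The planned shortening is also expressed in time. The target is 1.5 hours, and Appendix 2 says that "the time of infusion can be decreased by 30 minutes every third infusion". For the rate, the readable text of Appendix 2 sends the reader back to the section with the misprint: "The infusion rate will be adjusted according to Section 7.4 Study Drug Administration". The figure in that appendix is not shown in the public copy.

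**The concern.** Rate, volume and duration are tied together: any two determine the third. Section 7.3 lets the volume vary more than threefold, while 7.4 holds both the rate and the duration fixed. That can be true for one volume only. For a patient above 70 kg, a nurse who programs the pump by rate and one who programs it by time would give different infusions, and each could point to 7.4.

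Safety is the primary objective (Protocol 5.1), and infusion-related reactions (IRRs) are a listed safety endpoint. SAP 9.1.5 counts as an IRR a related event that starts during the infusion or within 2 hours of its end, so the time at risk depends on how long the infusion runs. If a site had used the printed rate, heavier patients would have had slower infusions and a longer IRR period than lighter ones. That would be worth knowing before IRRs are interpreted.

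**Working it through.** **Inputs.** Volumes of 150, 250 and 500 mL (Protocol 7.3); duration 3 hours = 180 minutes, and printed rate 0.83 mL/min (Protocol 7.4); IRR period = infusion plus 2 hours (SAP 9.1.5).

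**Reproducing the printed figure.** Rate = volume / minutes. 150 / 180 = 0.833 mL/min, which rounds to the printed 0.83. Neither of the other volumes gives it.

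**Rate needed for 3 hours, and the time taken at the printed rate.** Time = volume / 0.83.

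| Weight band | Volume | Rate for 180 min | Needed rate / 0.83 | Time at 0.83 mL/min | Time plus 2 h |
|---|---|---|---|---|---|
| up to 70 kg | 150 mL | 150/180 = 0.83 mL/min | 1.00 | 180.7 min = 3.0 h | 5.0 h |
| 70–100 kg | 250 mL | 250/180 = 1.39 mL/min | 1.67 | 301.2 min = 5.0 h | 7.0 h |
| above 100 kg | 500 mL | 500/180 = 2.78 mL/min | 3.35 | 602.4 min = 10.0 h | 12.0 h |

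The last two columns are conditional: they show what would follow if the rate were obeyed and the 3 hours ignored.

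**Which of the two instructions governs.** The Synopsis states 3 hours with no rate. Section 7.4 states 3 hours first and puts the rate in parentheses. Every scheduled change is given in hours or minutes, never in mL/min. All of this points to the duration as the instruction and the rate as a gloss that fits only the smallest volume.

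**How a longer infusion would reach the safety tables.** Under SAP 9.1.4, an event is timed by default from its onset and the recorded infusion stop. For an event that is also reported on the Drug Administration CRF and matched, the site's tick-box (during, within 2 hours, up to 24 hours) overrides that rule. A longer infusion could change which box is ticked, but recorded stop times do not alone decide the category. The event must also be rated as related to count as an IRR.

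**The case against.** The strongest reply is that no one would be misled. Three hours stands in the same sentence and in the Synopsis, and a 10-hour infusion would be questioned at once. The Appendix 2 figure may also list rates by volume. Much of this stands. It makes harm unlikely, and any error would be towards a slower infusion with the total dose unchanged. It does not make the parenthesis correct, and a correct figure in Appendix 2 would still conflict with 7.4 in two of the three weight bands.

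Three stronger readings are tempting, and the documents do not support them.

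- **Heavier patients were infused for 5 or 10 hours.** Nothing shows this. The documents give no weight distribution either, so even the number of patients above 70 kg is unknown.
- **IRRs are misclassified.** A related event during a longer infusion is still an IRR by the SAP's own definition. A longer period would affect how the counts are read, not whether they are valid.
- **The start of shortening is contradictory.** The Synopsis says "After the first 2 months of treatment with PRX-102, infusion time may be reduced gradually to 1.5 hours", while 7.4 says 3 months and 9.1.6 says Visit 7. The wording is permissive throughout, Appendix 8 places the evaluation of the rate reduction at infusion 7, and a start at Visit 7 satisfies every section. This is not a conflict.

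It is also fair to say that the SAP needs no new analysis to reveal a problem. SAP 8.8 summarizes infusion duration by visit and lists infusions with interruptions, and SAP 7.1 includes the minimum and maximum. An early infusion of 5 or 10 hours would show as a maximum, although not linked to weight.

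**Conclusion.** The inconsistency between 7.3 and 7.4 is certain as written. The printed rate is right for 150 mL and too low by factors of 1.67 and 3.35 for 250 and 500 mL. It is a minor error in an operative section. That the parenthesis, and not the duration, is wrong is an inference, but one that the Synopsis and the time-based shortening rules support well.

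Whether it affected any patient is unknown; the 5- and 10-hour infusions are a conditional worst case. The conclusion assumes only that the volumes in 7.3 are the volumes infused and that the rate in 7.4 applies to the whole infusion. Because the Appendix 2 figure cannot be seen, it cannot be said that volume-specific rates are absent from the protocol altogether. Dose per kilogram, sample size and the efficacy analyses are not touched.

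**What to change.** Keep 3 hours and delete the rate from 7.4. This is the simplest course, because the protocol manages infusions by time. Alternatively, give 0.83 / 1.39 / 2.78 mL/min for 150 / 250 / 500 mL. If rates are kept, the 1.5-hour rates are the volumes divided by 90: 1.67 / 2.78 / 5.56 mL/min. Check that the Appendix 2 figure agrees.

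The text change costs almost nothing, but by SAP 7.5 about 80% of patients had completed or discontinued by the interim analysis, so it will guide few remaining infusions.

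As an option, read the durations and infusion listing already planned in SAP 8.8 against the weight used to set the volume, for Visits 1 to 5, which precede any shortening. Values near 5 or 10 hours in the upper bands, with no recorded interruption or reaction, would suggest that the printed rate was used, and should be noted beside the IRR tables. Values near 3 hours in all bands would let the sponsor record that the misprint had no effect. This needs no new data and at most one cross-tabulation.

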7.5 Packaging and Labeling

PRX-102 is packed in vials containing 20 mg (2mg/ml), 0.7% NaCl and 25-30 mM Sodium Citrate (pH 5.7 - 6.3).

It is presented as a liquid stored in 15 ml clear injection glass vials (Müller + Müller-Joh. GmbH + Co, Germany). Grey rubber stoppers (formulation 4432/50/Grey) used for closure (West Pharmaceutical Services Duetschland GmbH & Co KG).

Sample Vial labels are provided in Appendix 1.

7.6 Conditions for Storage and Use

PRX-102 is stored at 2-8°C (36-46°F).

7.7 Dispensing, Compliance and Accountability

Protalix will provide drug accountability forms to assist the pharmacist in maintaining current and accurate inventory records covering receipt, dispensing, and the return of investigational drug supplies. When a shipment is received, the pharmacist will verify the quantities received and return the acknowledgment to the Protalix's CTM (Clinical Trial Material) coordinator. The drug will not be used without Protalix's approval in writing. The pharmacist investigational drug accountability record includes the identification of the person to whom the drug is dispensed, the quantity and the date of dispensing and any returned or unused drug, as well as full record of CTM storage temperature. This record is in addition to any drug accountability information recorded on the Case Report Form (CRF). These records will be readily available for inspection by a monitor and/or Protalix audits and are open to regulatory authority inspection at any time.

The investigator is responsible for maintaining accountability for the receipt, dispensing, and return of all study medication.

7.8 Prior and Concomitant Therapy

Medications having the potential to interfere with the evaluation of efficacy are excluded throughout the trial.

The following medications are strictly prohibited during the study treatment period:

- Fabrazyme® (agalsidase-beta)
- Replagal® (agalsidase alfa)
- Any other investigational or approved drug for treating Fabry disease

The use of premedication to prevent infusion reactions associated with agalsidase alfa initiated before entry to the study and recorded in the eCRF will be continued, but subjects will be titrated down over the course of the two months after switching to PRX-102. The rate of down titration/removal of the premedication will be at the investigator's discretion and recurrence of infusion reactions. Re-institution of premedication to manage infusion reactions will be allowed (see also Appendix 3 and 8).

Angiotensin-converting enzyme inhibitors (ACEIs) and angiotensin II receptor blockers (ARBs) at a stable dose for 4 weeks prior to entry into the study are allowed, but once a subject is randomized in the study, initiation of ACEI or ARB therapy is prohibited unless the subject develops proteinuria and the Protalix Medical Director approves. ACEI or ARB therapy may not be initiated for the treatment of hypertension in the absence of proteinuria.

8. EFFICACY AND SAFETY ASSESSMENTS

8.1 Safety Variable(s)

- Safety will be assessed by the frequency, severity, and duration of treatment-emergent AEs (see Section 8.3, Adverse Events), including clinically significant laboratory abnormalities, ECG changes from baseline, physical examination findings and assessment of the injection site after administration of the study drug
- Anti-Drug (i.e., PRX-102) IgG antibodies will be assessed before dosing with PRX-102 at baseline (Visit 1). Anti-PRX IgG antibodies will be assessed every month for the first 6 months and every 3 months until the end of study through the last infusion. If a patient continues treatment in an extension study, the anti-drug antibodies will be assessed as part of that study. For patients who end treatment with PRX-102, anti-PRX-102 antibodies will be assessed 1 and 3 months after last infusion
- Anti-Drug IgE antibodies will be assessed in events of hypersensitivity reaction following Sponsor request
- Ability to taper off infusion premedication at the start of the study
- Requirement for use of premedication overall to manage infusion reactions

